# 7.3. Premature Withdrawal from the Study

A patient has the right to withdraw from the study at any time, for any reason, and without repercussion.

The investigator and/or sponsor have the right to withdraw a patient from the study if it is no longer in the interest of the patient to continue in the study, or if the patient's continuation in the study places the scientific outcome of the study at risk (eg, if a patient does not or cannot follow study procedures). An excessive rate of withdrawals would render the study uninterpretable; therefore, unnecessary withdrawal of patients should be avoided.

Patients who are withdrawn prematurely from the study will be asked to complete the early termination visit, as described in Section 9.1.2.

Rules for discontinuation of study treatment (permanent or temporary) are discussed in Section 8.3.2.

# 7.4. Replacement of Patients

Patients prematurely discontinued from the study will not be replaced.

## 8. STUDY TREATMENTS

# 8.1. Investigational and Reference Treatments

REGN1908 and REGN1909 are each formulated in a buffered, aqueous solution at pH 5.8. REGN1908 and REGN1909 drug product will be supplied separately as lyophilized cakes in 20 mL glass vials.

REGN1908 and REGN1909 are provided individually in open-label vials in cartons. A medication numbering system will be used to label unblinded investigational study drug. Lists linking medication numbers with product lot numbers will be maintained by the groups (or companies) responsible for study drug packaging; these lists will not be accessible to individuals involved in study conduct. The unblinded pharmacist will prepare the unblinded investigational product and dispense it in a blinded manner to the blinded study staff for administration to the patient. Study drug will be stored at the site at a temperature of 2°C to 8°C. Storage instructions will be provided in the pharmacy manual.

For SC administration, these drug products are each reconstituted with 2.3 mL of sterile water for injection, yielding a final concentration of 100 mg/mL REGN1908 or 100 mg/mL REGN1909 in histidine, polysorbate 80, and sucrose. A total volume of 2.0 mL of the reconstituted liquid can be withdrawn from the glass vial. The reconstituted liquids will be mixed as a 1:1 cocktail. The resulting mixture will have a concentration of 100 mg/mL total of REGN1908-1909 (50 mg/mL REGN1908 and 50 mg/mL REGN1909). A 2.0 mL injection of the cocktail will provide a total dose of 200 mg REGN1908-1909. Three 2.0 mL SC injections will be administered for 600 mg total (300 mg per mAb). It is recommended that the 3 SC injections be given in separate locations, either the abdomen, thighs, or upper arms. During the treatment period, there will be 5 visits during which study drug will be administered for a total of 15 injections.

This is a multiple dose study. Study drug will be administered at study site Q12W for a total of 5 administrations. Patients will be randomized in a 1:1 ratio to receive 600 mg REGN1908-1909 or matching placebo that replaces REGN1908-1909.

Instructions on dose preparation are provided in the pharmacy manual.

## **8.2.** Rescue Treatments

Patients will be provided with the following medications (or an in-class equivalent, agreed upon with the sponsor) to treat allergic symptoms during the study:

- desloratadine 5 mg (second generation antihistamine)
- olopatadine 1 mg/mL (antihistamine eye drop)
- mometasone furoate 50 ug/dose (intranasal steroid)

From the time of baseline assessment period, patients can utilize the study provided allergy rescue medications (desloratedine, olopatadine and mometasone as specified above) to treat their allergic rhinitis and allergic conjunctivitis symptoms. During the baseline assessment and the efficacy assessment periods of the trial (weeks 0 to 12 and 48 to 60), daily use of rescue medications will be documented in the patient diary. At other non-efficacy periods (weeks 12 to 48), the rescue medication use can be documented in the concomitant medications.

Patients will be asked to refrain from taking specific prohibited medications during the study periods or within the specified time periods, preceding screening, baseline symptom and medication assessment, efficacy periods and at specific time points when skin testing or in-clinic spirometry will be conducted to prevent interference with the procedure (see Section 8.9.1).

# 8.3. Dose Modification and Study Treatment Discontinuation Rules

#### **8.3.1.** Dose Modification

Dose modification for an individual patient is not allowed.

# 8.3.2. Study Drug Discontinuation

Patients who permanently discontinue from study drug should be encouraged to remain in the study. Those who agree and do not withdraw from the study will be asked to return to the clinic for all remaining study visits per the visit schedule.

Patients who permanently discontinue from study drug and who opt to withdraw from the study will be asked to complete study assessments, per Section 9.1.2.

## 8.3.2.1. Reasons for Permanent Discontinuation of Study Drug

Study drug dosing will be permanently stopped in the event of:

- Evidence of pregnancy
- Serious or severe allergic reactions considered related to study drug
- A serious or severe asthma event deemed related to study drug that in the opinion of the PI would result in increased risk to the patient or a ≥50% decline in FEV1 from pre-treatment baseline
- If, in the investigator's opinion or at the specific request of the sponsor, continuation of study drug would be detrimental to the patient's well-being, or there is no longer any potential for benefit, or if continuation would undermine the scientific integrity of the study
- Specific types of liver dysfunction (eg, Hy's law is met (FDA, 2009))
- Patient withdraws consent/ assent
- In the event of an important protocol deviation, at the discretion of the investigator or the sponsor

## 8.3.2.2. Reasons for Temporary Discontinuation of Study Drug

Study drug dosing will be temporarily discontinued in the event of:

• An asthmatic patient experiencing an asthma exacerbation and/or has a clinically relevant decrease in FEV1 ≥20% below baseline at a visit during which study drug was scheduled to be dosed, per investigator judgement. In this case, the patient may return to the clinic within the dosing visit window to be re-assessed for eligibility to receive study drug.

- Neutrophil count  $\leq 1.0 \times 10^3 / \mu L$
- Sustained ALT/AST values greater than 3x the ULN plus total bilirubin >2x ULN or isolated AST/ALT >5x ULN
- Hospitalization
- Other intercurrent illness or adverse event or major surgery that could, in the opinion of the investigator, present an unreasonable risk to the patient as a result of his/her continued use of the study drug

After the condition leading to temporary discontinuation of study drug resolves, study drug dosing may resume. A decision to temporarily discontinue study drug and/or resume study drug dosing should be discussed with the Regeneron medical monitor.

The investigator may temporarily discontinue study drug dosing at any time, even without consultation with the medical monitor if the urgency of the situation requires immediate action and if this is determined to be in the patient's best interest. However, the Regeneron medical monitor should be contacted as soon as possible. Resumption of study drug dosing requires consultation and agreement between the investigator and the Regeneron medical monitor.

If a patient requires a prohibited medication at any time during the study, the principal investigator should contact the Regeneron medical monitor (except for illness requiring prompt treatment). Based on the discussions, study drug may be continued or temporarily or permanently discontinued.

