During the efficacy assessment periods, from the first day of dosing through the initial 12 weeks of the study and during the final efficacy assessment period (weeks 48 to 60), patients with comorbid asthma will complete the Asthma Daytime Symptom Diary (ADSD) and questions on asthma rescue medication use; this will occur each evening. Every morning, patients with co-morbid asthma will complete the Asthma Nighttime Symptom Diary (ANSD), and questions on nighttime awakening. In-clinic spirometry and ACQ-5 will be collected in patients with co-morbid asthma to compare any changes between baseline and the end of the initial 12-week efficacy assessment and the last 12 weeks of the treatment period.

[figure not shown]

Figure 1: Study Flow Diagram

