# 9. STUDY SCHEDULE OF EVENTS AND PROCEDURES

## 9.1. Schedule of Events

In light of the public health emergency related to COVID-19, the continuity of clinical study conduct and oversight may require implementation of temporary or alternative mechanisms. Examples of such mechanisms may include, but are not limited to, any of the following: phone contact, virtual visits, telemedicine visits, online meetings, non-invasive remote monitoring devices, use of local clinic or laboratory locations, and home visits by skilled staff. Additionally, no waivers to deviate from protocol enrollment criteria due to COVID-19 will be granted. All temporary mechanisms utilized, and deviations from planned study procedures are to be documented as being related to COVID-19 and will remain in effect only for the duration of the public health emergency.

Study assessments and procedures are presented by study period and visit in Table 3.

**Table 3:** Schedule of Events

	Screening	Period 	Randomization				Doubl	e-Blino	l Trea	tment l	Period			Follow Up	Period	
				Initial Efficacy Assessment								Final (Primary) Efficacy Assessment		End of Treatment (EOT)/ Early Term.	End of Study (EOS)	
Visit	Screening Visit 1 	Baseline V2 	R V3 	Tel V4	Tel V5	V6	Tel V7	V8	Tel V9	V10	Tel V11	V12	Tel V13	EOT V14	EOS V15	Un- scheduled Visit 
Day	-85 t	o -1	1	8	43	85	127	169	211	253	302	337	365	421	505	
Window (day)				±3	±7	±14	±7	±14	±7	±14	±7	±14	±7	±7	±7	
Week	- 12		0	1	6	12	18	24	30	36	43	48	52	60	72	
Screening/Baseline:	•												 	•	'	l
Inclusion/exclusion	X	X	X													
Informed consent/assent	X															
Medical history	X															
Demographics (age, race, height, weight)	X															
Skin prick test for cat and HDM 	X³					X								X	X	
Skin prick test for other allergens 	X³															
Dispense e-diary		X										X				
Collect e-diary						X								X		
Dispense rescue meds		X	X			X		X		X		X				
Randomization 			X										_			
Treatment:										,						
Administer study drug 			X			X		X		X		X				
Concomitant meds and treatment	X	X	X	X	X	X	X	X	X	X	X	X	X	X	X	X

	Screening				Doubl	e-Blind	l Trea	tment l	Period			Follow Up	Period			
				Initial Efficacy Assessment								Final (Primary) Efficacy Assessment		End of Treatment (EOT)/ Early Term.	End of Study (EOS)	

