Visit	Screening Visit 1 	Baseline V2 	R V3 	Tel V4	Tel V5	V6	Tel V7	V8	Tel V9	V10	Tel V11	V12	Tel V13	EOT V14	EOS V15	Un- scheduled Visit 
Day	-85 to	o -1	1	8	43	85	127	169	211	253	302	337	365	421	505	
Window (day)				±3	±7	±14	±7	±14	±7	±14	±7	±14	±7	±7	±7	
Week	- 1	2	0	1	6	12	18	24	30	36	43	48	52	60	72	
Efficacy:	-				L	 				.					.	
TNSS, TOSS, DMS		X	Nightly i	n e-dia	ary							N	ightly in			
PGIS			X			X								X		
PGIC						X										
RQLQ(S)			X			X						X		X		
Evaluation of cat exposure						X		X		X		Daily in e-diary				X
Patient Experience Assessment														X		
Spirometry 	$X^6$		$X^6$			$X^7$						$X^7$		$X^7$		
ACQ-5 for asthma patients 			$X^6$			X 						$X^7$		$X^7$		
ANSD and nighttime awakening for asthma patients 		$X^7$	Daily in	e-diar	y 							Daily in e-diary 				
ADSD and asthma rescue med use for asthma patients 		X 	Nightly i	n e-dia	ıry 							N	ightly in 6	e-diary 		
Safety:					1			- 0			ı	2				
Vital signs 	X	X	X 			$X^8$		$X^8$		$X^8$		X8		X	X	X
Physical examination	X		X			X		X		X		X		X	X	X
ECG	X											-				X
Adverse events	X ←														>	· X

	Screening	Period 	Randomization				Doubl	e-Blind	l Treat	tment l	Period			Follow Up		
				Initial Efficacy Assessment									nal nary) cacy sment	End of Treatment (EOT)/ Early Term.	End of Study (EOS)	
Visit	Screening Visit 1 	Baseline V2 	R V3 	Tel V4	Tel V5	V6	Tel V7	V8	Tel V9	V10	Tel V11	V12	Tel V13	EOT V14	EOS V15	Un- scheduled Visit 
Day	-85 to	o -1	1	8	43	85	127	169	211	253	302	337	365	421	505	
Window (day)				±3	±7	±14	±7	±14	±7	±14	±7	±14	±7	±7	±7	
Week	- 1	2	0	1	6	12	18	24	30	36	43	48	52	60	72	
Laboratory Testing:																
Hematology	X					X		X		X		X		X		X
Blood chemistry	X					X		X		X		X		X		X
Serum pregnancy test for WOCBP	X															X
Urine pregnancy for WOCBP 		X	X			X		X		X		X		X		X
FSH test for postmenopausal women only 	X															
Urinalysis	X															X
Serum for specific IgE for Fel d 1 and cat	X		X													
Serum for sIgE for Fel d 2, 4, and 7			X			X								X		
Serum for sIgE for other allergens (eg, HDM, etc)	X		X													
PK and ADA:																

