- 3. Screening skin prick test for cat hair and skin prick test for other relevant allergens (such as house dust mite [HDM] and other relevant allergens) is performed as described in the study manual. If screening skin prick test for cat hair is negative at screening visit 1 (mean wheal diameter less than at least 5 mm greater than a negative control), then other screening visit 1 procedures do not need to be performed as the patient will have failed screening based upon cat hair skin prick testing (eg, perform skin prick testing prior to other procedures such as blood draw, spirometry, etc). Appropriate measures will be taken to prevent accidental unblinding during the treatment period when skin prick tests are performed.
- 4. Randomization may occur within 1 day prior to study drug administration. All safety assessments performed at screening must be normal and checked against the inclusion/exclusion criteria prior to study drug administration.
- 5. Patients will remain in the clinic for 2 hours post-drug administration after receiving the first dose of study drug and after all subsequent doses.
- 6. All patients will undergo in-clinic spirometry during screening and at randomization. After randomization, spirometry will only be done in patients with asthma. Washout of bronchodilator medications will be discussed by investigator with the patient and verified before performing the measurements as specified in Section 9.2.2.10. During the treatment period, at a visit for which study drug dosing is scheduled, any patient with asthma

experiencing an asthma exacerbation and/or has a clinically relevant decrease in FEV1  $\geq$ 20% below baseline will not be dosed, per investigator judgement. In this case, the patient may return to the clinic within the permitted dosing window to be re-assessed for eligibility to receive study drug.

- 7. Only in patients with asthma: ANSD, ADSD, nighttime awakenings, asthma rescue medication use, ACQ-5, and post-randomization spirometry assessments will be collected.
- 8. For all in-clinic visits where study drug is administered at visit 3, visit 6, visit 8, visit 10, and visit 12 vital signs are taken twice: (1) prior to study drug administration, and (2) at approximately 2 hours after completion of the injections.

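### Does the FEV1 dosing hold for asthma patients fail at weeks 24 and 36 because no spirometry is scheduled there?

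*Protocol*

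**What the plan says.** Protocol Section 8.3.2.2 lists reasons to pause study drug. For asthma patients there are two, joined by and/or: an exacerbation, or a "clinically relevant decrease in FEV1 ≥20% below baseline at a visit during which study drug was scheduled to be dosed". Both are left to investigator judgement, and the patient may come back within the dosing window to be re-assessed. Footnote 6 to Table 3 repeats the rule: "at a visit for which study drug dosing is scheduled, any patient with asthma" who meets either condition is not dosed, again on the investigator's judgement.

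Footnote 8 fixes the dosing visits: "study drug is administered at visit 3, visit 6, visit 8, visit 10, and visit 12". The Table 3 spirometry row is marked at visits 1, 3, 6, 12 and 14, and Section 9.2.2.10 ties spirometry to the Table 3 time points. Section 6.1 gives a purpose for the post-randomization measurements: "In-clinic spirometry and ACQ-5 will be collected in patients with co-morbid asthma to compare any changes between baseline and the end" of each efficacy period.

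Section 8.3.2.1 has a second FEV1 threshold, for permanent discontinuation: a "≥50% decline in FEV1 from pre-treatment baseline".

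**The concern.** The hold is worded for every scheduled dosing visit and exempts none. Because of the and/or, the FEV1 trigger stands apart from the exacerbation trigger, and a 20% fall cannot be judged without an FEV1 value. Two of the visits it covers have no scheduled spirometry.

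The contrast within the same list makes this look like an oversight. The neutrophil and liver-enzyme hold criteria have hematology and chemistry scheduled at visits 8 and 10. The history for Amendment 3 shows that the week 24 and 36 blood tests and the asthma hold arrived in the same amendment, the hold being meant to avoid dosing when it would be unwise. Neither the ACQ-5 nor the asthma diary covers visits 8 and 10: the row "ACQ-5 for asthma patients" is marked at visits 3, 6, 12 and 14, and the row "Collect e-diary" at visits 6 and 14, with the diary handed out again only at visit 12.

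At stake would be a dose given to an asthma patient with an unnoticed fall in lung function, and sites differing on whether dosing without an FEV1 complies with the protocol.

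**Working it through.** No sample size, power or alpha figure bears on this point. The check is a column count of protocol Table 3, followed by a reading of the rule.

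**Inputs.** Visit days, windows and marks come from Table 3, and the dosing visits are confirmed by footnote 8.

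| Visit | Week | Day | Study drug | Scheduled spirometry |
|---|---|---|---|---|
| 3 | 0 | 1 | yes | yes (baseline) |
| 6 | 12 | 85 | yes | yes |
| 8 | 24 | 169 | yes | no |
| 10 | 36 | 253 | yes | no |
| 12 | 48 | 337 | yes | yes |
| 14 | 60 | 421 | no | yes |

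**Count.** Dosing visits {3, 6, 8, 10, 12} less spirometry visits {1, 3, 6, 12, 14} leaves {8, 10}. Visit 3 supplies the baseline, so a fall can first be seen at visit 6. The gap is 2 of 4 post-baseline doses.

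**Age of the last scheduled FEV1.** Visits 6, 8, 10 and 12 each have a ±14-day window, so an interval between two of them can move by ±28 days.
- Visit 8: 169 − 85 = 84 days (56 to 112).
- Visit 10: 253 − 85 = 168 days (140 to 196).
- Whole gap, visit 6 to visit 12: 337 − 85 = 252 days (224 to 280).

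**Patients who could be concerned.** The Introduction expects at least 30% with asthma: 0.30 × 630 = 189. This counts asthma patients, not missed falls.

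**Does the rule conflict with the schedule?** Section 8.3.2.2 and footnote 6 say what happens if a fall is present; neither orders an FEV1 before each dose. Table 3 sets routine testing. A site can obey both. Footnote 6 is attached to the spirometry row and deals with when spirometry is done and with bronchodilator washout before it states the hold. Read there, it naturally means that a dose is held if spirometry at a dosing visit shows the fall.

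**What is in place at visits 8 and 10?** Table 3 schedules vital signs, physical examination, adverse event and concomitant medication review, hematology and chemistry. Telephone visits 7, 9 and 11 fall between the doses. Section 10.1.3 makes an asthma exacerbation reportable within 24 hours. Section 8.3.2.2 also lets the investigator pause dosing at any time, and Section 9.1.3 allows unscheduled visits.

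**Does an analysis need the missing values?** The FEV1 endpoints (protocol Section 4.2) are at weeks 12 and 60. Under SAP Section 6.5 a discretionary reading, if handled as unscheduled, is not mapped beyond 6 weeks (42 days) from the target day. At nominal days, visit 8 falls in the visit 6 window, 169 − 85 = 84 days from target. Visit 10 falls in the visit 12 window, 337 − 253 = 84 days from target. Both exceed 42, so such readings would not enter the FEV1 analysis. For the primary endpoint, SAP Table 4 uses all data collected after study drug is stopped.

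**The case for a change.** The best argument for acting is that judgement needs something to judge. Leaving the decision to the investigator does not produce an FEV1, and the discretion in Section 9.1.3 and footnote 13 is written for unscheduled visits, whereas visits 8 and 10 are scheduled. Spirometry also needs bronchodilator washout, with examples in Section 9.2.2.10 from 6 to 24 hours, so a patient not warned beforehand may arrive unable to give a usable reading. None of the other safeguards measures FEV1. A line saying that the trigger applies only where a value exists would cost little.

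Much of this stands. The count is right, the wider reading of footnote 6 is possible (the post-randomization spirometry cells carry footnote 7, and the wording refers to any dosing visit), and the text does not say which reading is meant. Three parts are weaker:
- Section 9.2.2.10 says that a separate operational manual gives sites the spirometry details. It is not among the documents, so it cannot be concluded that sites lack instruction.
- The 50% threshold in Section 8.3.2.1 sits in an item that opens with a serious or severe drug-related asthma event. On its face it is driven by an event; it names no dosing visit and does not refer to Table 3.
- The purpose given in Section 6.1 is not stated to be the only one. The hold's place on the spirometry row suggests that the readings also inform dosing.

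**Conclusion.** The gap is real but narrow: one of two asthma triggers lacks a scheduled measurement at 2 of 4 post-baseline doses. It is not a contradiction, because a conditional rule and a routine schedule can both be followed. Sites can fill the missing detail by clinical judgement, supported by the examination, the history and the exacerbation trigger at the same visits.

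A wording clarification would alter no endpoint, estimand or planned analysis. Only added spirometry at weeks 24 and 36 would put a planned reading behind the trigger there. That is an extra procedure and a clinical decision for the sponsor, on which no view is taken here. The documents offer no rate of undetected falls to weigh against its burden.

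This rests on two assumptions: that the hold is read as conditional, and that nothing in the unseen spirometry manual contradicts Table 3. If the protocol is amended for other reasons, a line on when the FEV1 trigger applies would be a courtesy to sites, not a correction.

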# 8.4. Management of Acute Reactions

## **8.4.1.** Acute Injection Reactions

## **8.4.1.1.** Systemic Injection Reactions

Emergency equipment and medication for the treatment of systemic reactions must be available for immediate use. All injection reactions must be reported as AEs (as defined in Section 10.2.1) and graded using the grading scales as instructed in Section 10.2.4.

Acute systemic reactions following SC injection of study drug should be treated using clinical judgment to determine the appropriate response according to typical clinical practice.

#### **8.4.1.2.** Local Injection Site Reactions

Local injection site reactions must be reported as AEs and graded according to Section 10.2.4.

# 8.5. Method of Treatment Assignment

Approximately 630 patients will be randomized in a 1:1 ratio to receive either 600 mg (300 mg per mAb) REGN1908-1909 or placebo according to a central randomization scheme provided by an interactive voice response system (IVRS)/interactive web response system (IWRS) to the designated study pharmacist (or qualified designee). Randomization will be stratified according to age (adolescents vs adults), asthma status (yes vs no), and house dust mite (HDM) sensitivity (<0.7 kUa/L versus ≥0.7 kUa/L).

